8.1. Primary objective(s)

The primary objective is to investigate overall survival.

8.2. Secondary objective(s)

Secondary objectives are to determine:

- progression free survival (either clinical progression and/or radiological progression)
- time to progression (either clinical progression and/or radiological progression)
- disease control rate
- duration of Stivarga[®] treatment
- tumor status at different visits
- incidence of treatment emergent adverse events

Additionally possible prognostic factors e.g. presence of severe comorbidities, metastatic sites, early relapse after adjuvant treatment, and KRAS mutation will be evaluated.

9. Research methods

9.1. Study design

This study is a prospective, open-label, multi-center, single arm cohort non-interventional post-authorization safety study of patients with mCRC who are prescribed Stivarga[®]. The study will be conducted in Germany. The study will start after Stivarga[®] has been authorized and made commercially available in Germany. All patients for whom the selection criteria are fulfilled are eligible for enrollment into the study. Patient's clinical information will be documented at time of the initial visit and at time of follow-up visits which should be documented every 4 to 6 weeks.

The actual treatment duration will be determined solely by the physician. Patient data will be collected according to local clinical practice during personal or phone visits. The study ends 12 months after enrollment of the last patient. Serious adverse events will be followed up until resolution.

A prospective, non-interventional design was chosen as up to now no data are available on real-life treatment with Stivarga[®].

9.1.1. Primary endpoint(s)

The primary endpoint is overall survival (OS). OS is defined as the time interval from start of Stivarga® therapy to the date of death due to any cause. Patients alive or lost to follow-up at the time of analysis will be censored at the last date known to be alive.

9.1.2. Secondary endpoint(s)

The secondary endpoints are:

- Progression free survival (PFS) is defined as the time interval measured from the day of start of Stivarga® treatment to diagnosed (radiological or clinical) progression or death, whichever comes first. Progression-free survival for patients without disease progression or death at the time of analysis will be censored at the last date of tumor evaluation.
- Time to progression (TTP) is defined as the time interval from start of Stivarga® therapy to the date of diagnosed (radiological or clinical) progression. Patients without tumor progression at the time of analysis will be censored at their last date of tumor evaluation.
- Disease control rate (DCR) is defined as percentage of patients, whose best response was not progressive disease (i.e. complete response, partial response or stable disease).
- Duration of Stivarga® treatment is defined as the time interval from start of Stivarga® therapy to the date of permanent discontinuation of Stivarga® therapy (regardless of the reason for discontinuation). It will be calculated as last dosing date - first dosing date + 1. A patient with only one dose of Stivarga® will be considered as having a treatment duration of one day.
- The tumor status at different visits will be evaluated according to the categories “complete response”, “partial response”, “stable disease”, “progressive disease by clinical judgment”, “progressive disease measurement proven”, “unknown” and “not applicable”. The best overall response will be analyzed providing absolute and relative frequencies of the tumor status categories.
- Incidence of treatment-emergent adverse events (TEAE) - patients will be monitored for TEAEs using the NCI-CTCAE Version 4.03. Detailed information collected for each TEAE will include: a description of the event, duration, whether the TEAE was serious, relationship to Stivarga®, action taken, clinical outcome. Summary tables will present the number of subjects observed with TEAEs and corresponding percentages. Additional subcategories will be based on event intensity and relationship to study drug.

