9.2.4. Withdrawal

Each patient has the right to refuse further participation in the study at any time and without providing any reasons. A patient's participation is to be terminated immediately upon his/her request. The investigator should seek to obtain the reason and record this on the Case Report Form (CRF). In this non-interventional study, withdrawal from the study is independent of the underlying therapy. On the other hand, premature end of therapy does not automatically imply end of documentation: Follow-up continues at least 30 days after end of therapy.

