9.2.7. Visits

The start of the study is the date from which information on the first study patient can be first recorded in the study dataset (first patient first visit). A visit is defined as any status assessment or new treatment decision the treating physician takes with the presence of the patient.

The investigator should document at least an initial visit, follow-up visits and a final visit for each patient in the case report form (CRF). Follow-up assessment should be documented every 4 to 6 weeks, although the patient's visit schedule itself will be at the treating physician's discretion. A certain number or frequency of visits is not requested by this protocol, however at least an initial visit and a final visit must be documented.

The observation period for each patient covers the period from start of Stivarga®-therapy to death. The median observation period per patient is estimated to be about 7 months, the study will end 12 months after last patient first visit (also see Section 9.5). The final data collection per patient is at patient's death, at end of study or at any time due to premature discontinuation of observation (whatever is earlier). If the documentation is stopped prematurely, the reasons for the end of observation have to be given. If a patient joins an interventional clinical study during the course of observation, at least the information on survival will still be collected up to the end of this study.

If a patient will still be alive at time of study closure, this will be documented at final observation.

The CRF is available upon request. The respective document is listed in Annex 1.

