9.3. Variables

The investigator collects historic data (demographic and clinical characteristics) from medical records if available, or else by interviewing the patient. Likewise, the investigator collects treatment related data during initial visit and follow-up visits.

Table 2: Tabulated overview on variables collected during the study

Schedule Procedure	Base-line	Initial visit	Follow-up	End of therapy	End of observation	Follow-up after end of therapy
Visit date	X	X	X	X	X	X
Patient information and consent	X					
Demographic data	X					
Date of initial CRC diagnosis	X					
Medical history of CRC	X					
Previous treatment for CRC	X					
Concomitant diseases	X					
Weight and height		X				
Tumor status		X				
Performance status (ECOG)		X	X	X	X	
Start of Stivarga® treatment		X				
Initial dose of Stivarga®		X				
Blood pressure		X*				
Laboratory values**		X	X	X	X	
Change of therapy since last visit			X	X	X	
Tumor status evaluation			X	X	X	
Concomitant radiotherapy			X	X	X	
Concurrent diagnostic and therapeutic procedures for mCRC			X	X	X	
Treatment (preventive or therapeutic) for hand foot skin reaction		X	X	X	X	
Concomitant medication		X	X	X	X	
Adverse Events			X	X	X	X***
Date of last Stivarga® dose				X	X	
Reason for discontinuation of treatment				X		
Reason for end of observation					X	
Survival assessment						X
Further treatment for mCRC						X

* weekly up to six weeks from start of therapy

** only documented if new information is available from regular practice. No additional diagnostics are required for the study.

*** for Stivarga®: up to 30 days after end of treatment

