9.3.12. Survival status after end of therapy

Typical information to be collected at follow-up after end of therapy includes:

- Request for survival status performed
 - If no: reason for no assessment
 - If yes: survival status
- Documentation of AEs for up to 30 days after last Stivarga[®] intake
- Further anti-cancer therapy (medication) during follow-up
 - Any systemic treatment, if yes, please specify experimental drug or other

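### Survival but not progression is scheduled after end of therapy, so PFS at the final analysis is biased upward for patients who stop before progression and later die

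*Protocol*

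**What the plan says.** Protocol section 9.1.2 measures PFS from start of Stivarga "to diagnosed (radiological or clinical) progression or death, whichever comes first". It sets no limit on the time between the last tumor evaluation and a death that counts. Censoring applies only to patients with neither event: "Progression-free survival for patients without disease progression or death at the time of analysis will be censored at the last date of tumor evaluation". TTP is censored at the last tumor evaluation in the same way, but death is not a TTP event.

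In Table 2 (section 9.3), the row "Tumor status evaluation" is ticked at follow-up, at end of therapy and at end of observation. It is blank in the column for follow-up after end of therapy. The row "Survival assessment" is ticked in that column only. Section 9.3.12 agrees with the table. It begins "Typical information to be collected at follow-up after end of therapy includes" and lists survival status, adverse events to 30 days and further anti-cancer therapy, with no progression item.

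Three statements bear on what else might be recorded:
- Section 9.2.4: "Follow-up continues at least 30 days after end of therapy".
- Section 9.2.7: "The observation period for each patient covers the period from start of Stivarga®-therapy to death".
- Section 9.2.7 also places final data collection at death, "at end of study or at any time due to premature discontinuation of observation", whichever is earliest.

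**The concern.** After therapy ends, the schedule follows one component of PFS (death) and not the other (progression). Section 9.1 leaves treatment duration to the physician, and section 9.1.2 defines it regardless of the reason for stopping, so patients can stop before progression.

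Take a patient who stops at month 1 with stable disease, progresses at month 3 and dies at month 8. True PFS is 3 months. If the progression is not dated, recorded PFS is 8 months.

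This is a single-arm study, so the PFS curve itself is the result and no control arm shares the bias. Section 9.9 says comparison is possible only with historical clinical-study data, and a late-shifted curve would look favorable there. Section 9.9 warns about variable visit intervals and the quality of tumor evaluation, but not about this gap.

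**Working it through.** **The plan's own figure.** The protocol states no PFS figure. Its OS assumptions (section 9.5) supply the survival input, so they were checked first:
- S(12) = 0.5^(12/6.4) = 0.273, so 72.7% die within 12 months.
- Deaths = 500 × 0.80 × 0.727 = 290.9, or 500 × 0.80 × 0.73 = 292.0 with the rounded rate. The stated 292 is reproduced.
- Wald interval with n = 400: 0.273 ± 1.96 × √(0.273 × 0.727/400) = (22.9%, 31.6%), matching the stated (23%, 32%).

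**Inputs for the PFS check.**
- From the protocol: median OS of 6.4 months (9.5), follow-up of at least 12 months after the last enrollment (9.1), and the PFS event and censoring rules (9.1.2).
- Assumed, because the protocol gives no figure: exponential time to progression with median 1.5, 2 or 3 months; 10% to 40% stopping before progression, independently of prognosis; death without progression at 0.01 per month; no progression recorded after stopping.

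**Method.** 200,000 patients were simulated, with post-progression survival calibrated to the 6.4-month median OS. Kaplan-Meier PFS with every progression date known was compared with the protocol rule. Under that rule, a patient who stops early has an event at death if death falls within follow-up, and is otherwise censored at stopping.

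**Final analysis, 2-month median time to progression, no capture after stopping.** True median PFS is 1.95 months and true 6-month PFS is about 11.8%.

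| Stopping early | Median, protocol rule (months) | 6-month PFS, protocol rule | Rise in 6-month PFS (points) |
|---|---|---|---|
| 10% | 2.02 | 15.3% | 3.5 |
| 20% | 2.13 | 19.0% | 7.2 |
| 30% | 2.28 | 23.2% | 11.4 |
| 40% | 2.57 | 27.6% | 15.8 |

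Across 10% to 40% stopping, a 1.5-month median time to progression takes median PFS from about 1.47 to 1.52–1.99 months. A 3-month median takes it from about 2.87 to 2.98–3.55 months.

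**Partial capture (2-month median, 20% stopping).** With half of the later progressions dated, the median goes from 1.95 to 2.04 months and 6-month PFS from about 12% to 15.5%. With 80% dated, the median goes from 1.94 to 1.98 months and 6-month PFS from about 12% to 13%.

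**Loss of contact.** With 12 months of follow-up and survival never obtained for 20% of early stoppers, the median goes from 1.94 to 2.00–2.29 months across 10% to 40% stopping.

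**Short follow-up.** With 3 months of follow-up and 40% stopping, the median is essentially unchanged (1.95 against 1.94 months), and 3-month PFS falls from 34.3% to 31.8%. With 6 months and 40% stopping, the median rises from 1.95 to 2.12 months, but 6-month PFS falls from 11.8% to 6.5%. The reason is that stoppers who die soon stay in as events, while stoppers still alive are removed back at their last evaluation.

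**TTP.** With 20% stopping independently of prognosis, median TTP is 2.00 months with full dates and 2.00 months under the protocol rule. Progressions after stopping are censored, not misdated.

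**The case against.** The strongest reply is that progression after therapy may well be recorded. Table 2 ticks tumor status at end of observation, a column separate from end of therapy. Observation is meant to run to death, documentation continues for at least 30 days after therapy, and the list in 9.3.12 is only a typical one. Section 9.3.11.2 records an assessment date with tumor status, and section 9.4 asks for results from other physicians. The CRF is not shown. A reader might infer that progression is never collected after therapy; these passages do not support that. What stands is that a single closing entry, usually at death or study end, does not clearly ask when progression first occurred, and the column meant for post-therapy follow-up leaves it out.

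Three other stronger readings also fail:
- That PFS runs to death for everyone who stops early. It does so only for those who die; survivors are censored at their last evaluation.
- That this early censoring of survivors adds to the inflation. It pulls PFS down, which is why short follow-up can cancel or reverse the bias.
- That TTP is biased as well. It loses events and precision, but no bias appears if stopping is independent of prognosis.

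It is also fair that counting death whenever it occurs is ordinary PFS practice, that section 9.7.1 leaves derived variables and missing data to the SAP, and that section 9.9 already urges caution with PFS. But an analysis plan cannot recover dates that were never collected, and the caution in 9.9 concerns other problems. The median shift is small, at most 0.3 month with up to 30% stopping and a 2-month median, which is less than the 4-to-6-week documentation interval. The 6-month rate moves more.

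**Conclusion.** The concern holds in this limited form. The collection schedule and the PFS definition do not match, and at the final analysis the mismatch raised PFS in every setting tried.

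The amount cannot be fixed from the protocol, which gives neither a median PFS nor the share stopping before progression. With a 2-month median time to progression, 10% to 30% stopping early and no later capture, the rise is about 0.1 to 0.3 month in the median and 3 to 11 points at 6 months. With 20% stopping and half of later progressions captured, it is about 3 to 4 points at 6 months. These figures also assume that stopping is independent of prognosis and that follow-up is at least 12 months.

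The direction is not assured at the July 2016 efficacy interim. Enrollment runs to 31 July 2016, so recent enrollees will have little follow-up then and the bias may be nil or reversed. PFS is a descriptive secondary endpoint and OS is untouched. The change is worth making, but the point does not threaten the study's primary result.

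**What to change.** 1. Reconcile Table 2 with section 9.3.12 by adding one item to the post-therapy follow-up form: date and type (clinical or radiological) of first documented progression. It should come from routine records with no extra imaging, and be back-filled where records allow.
2. Add a PFS sensitivity analysis that censors at the last tumor evaluation when death follows a long gap without evaluation, for example more than two documentation intervals (2 × 6 = 12 weeks at the upper end of the 4-to-6-week range). Keep the current definition as the main analysis. In the simulation, censoring every early stopper at the last evaluation returned the true median (1.95 against 1.95 months), but only because stopping was independent of prognosis. In practice this censoring may be informative, so it is a check and not a replacement.
3. Name the gap in section 9.9, including that its direction can differ at the interim.

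Cost: one CRF item, back-filling for patients already off therapy, and fewer PFS events in the sensitivity analysis. With version 3.0 dated April 2016 and enrollment closing in July 2016, back-filling would reach much of the cohort, so it is more work than a single field suggests.

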9.5. Study size

Assuming an exponentially distributed OS with a median of 6.4 months, approximately 73% of patients are expected to die within a 12 months observation period. It is aimed to enroll 500 patients in this study. With 500 patients and a loss-to-follow-up of 20% of patients approximately 292 deaths will be observed in a 12-months-time-period. This means that under these assumptions, the 95% confidence interval for the 1-year survival rate of 27% would be approximately (23%, 32%), i.e. of length 9 percentage points. This time frame and number of events seem to be reasonable to describe the Kaplan-Meier-curve for overall survival in the routine daily practice conditions adequately, in particular considering the fact that the pivotal phase III study CORRECT had similar patient numbers randomized to the regorafenib treatment arm (n=505 regorafenib patients valid for ITT analysis).

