9.7.3. Analysis of treatment data

Descriptive statistics will be calculated for the treatment duration. The following frequencies will be calculated: the number of patients with dose reductions, number of patients with dose interruptions, total number of dose reductions and frequencies of reasons for reduction, total number of dose interruptions and frequencies of reasons for interruption.

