9.7.5. Analysis of secondary outcome(s)

Descriptive summaries of KM estimates (including number of failed, number censored, 25th and 75th percentiles with respective 95% CI and median with 95% CI) and KM curves will be presented for time-to-event effectiveness variables (TTP, PFS). Summary statistics will be calculated for duration of Stivarga[®] treatment.

Disease control rate, defined as percentage of patients whose best response was not progressive disease (i.e. complete response, partial response or stable disease), and the corresponding 95% confidence interval will be calculated.

Category counts and frequencies (percentages) will be calculated for tumor status at different visits and best overall tumor response.

AEs will be summarized using the MedDRA and the CTCAE coding system. Event rates for single AEs will be calculated based on the total number of patients valid for safety. AEs will be categorized according to relation, seriousness, CTCAE grade (version 4.03), discontinuation of therapy, action taken and outcome. Special attention will be paid to SAEs and unexpected or unlisted ADRs.

The analyses described in this section will be performed on treatment-emergent AE. Events which are not treatment-emergent will be tabulated without further stratification. All patients will be presented with all details from the AE report form. Further details of the safety analysis will be described in the SAP.

Subgroup analyses stratified with prognostic/predictive factors collected at baseline may be explored.

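### Duration of Stivarga treatment is a time-to-event endpoint summarised without censoring, so unfinished treatment counts as complete; minor at closure, larger if reported at the July 2016 interim

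*Protocol*

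**What the plan says.** Section 9.1.2 of the protocol defines treatment duration from the start of therapy "to the date of permanent discontinuation of Stivarga® therapy (regardless of the reason for discontinuation") and gives the formula: "It will be calculated as last dosing date - first dosing date + 1". It has no rule for a patient who has not permanently discontinued.

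The analysis sections then fix the method. Section 9.7.3: "Descriptive statistics will be calculated for the treatment duration". Section 9.7.5: "Summary statistics will be calculated for duration of" Stivarga treatment. The abstract (section 4) makes the same split, with Kaplan-Meier for OS, TTP and PFS and descriptive statistics for duration.

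The other interval endpoints are handled differently. For OS, section 9.1.1 says "Patients alive or lost to follow-up at the time of analysis will be censored at the last date known to be alive". For TTP, section 9.1.2 says "Patients without tumor progression at the time of analysis will be censored at their last date of tumor evaluation", and PFS has a parallel rule.

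Three further provisions matter:

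- Table 2 in section 9.3 collects the date of the last Stivarga dose at end of therapy and also at end of observation.
- Section 9.7.1 includes every patient with at least one dose, plans an interim analysis of efficacy and safety data in July 2016, and leaves derived variables and missing-data handling to the SAP.
- Section 9.2.7 ends the study 12 months after last patient first visit, which section 6 puts at 31 July 2016.

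**The concern.** An interval that ends at permanent discontinuation is a time-to-event variable. The study closes on a fixed date, treatment length is at the physician's discretion, and some patients will be lost. For a patient still on drug at a cut-off, or lost on drug, last minus first dosing date + 1 measures treatment so far, not treatment duration as section 9.1.2 defines it. A mean or quantile that mixes these values with completed durations can only be too low or, at best, unaffected.

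Duration is a listed secondary objective, and section 9.1 justifies the study by the lack of real-life treatment data. A figure that is too short would be read as how long patients in routine practice stay on the drug. No hypothesis test, sample size or primary result depends on it.

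**Working it through.** **The protocol's own figure.** It gives no expected treatment duration, so there is none to reproduce. The nearest calculation is in section 9.5, which starts "Assuming an exponentially distributed OS with a median of 6.4 months". It reproduces: 1 − 2^(−12/6.4) = 72.7%, and 500 × 0.8 × 0.73 = 292 deaths. It is unaffected by this point, but it shows where the 20% loss comes from: a count of deaths over 12 months, not a statement about loss during treatment.

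**Inputs from the protocol.** Start Q4 2013; last patient first visit 31 July 2016; interim July 2016; closure 12 months after last enrolment; 20% loss over 12 months.

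**Assumptions.** Exponential treatment duration T with true median m = 2, 3 or 4 months. Uniform entry from mid-Q4 2013 to the end of July 2016, which is 32.5 months. Unfinished patients enter with the time observed so far, min(T, C), where C is the time from entry to cut-off or loss.

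**Method.** The median of the plain summary solves P(T > t) × P(C > t) = 0.5, with P(T > t) = 2^(−t/m). Because T is exponential, the mean of min(T, C) equals the true mean m/ln 2 times the share who have discontinued. The relative fall in the mean is therefore the share still on treatment or lost on treatment.

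**July 2016 interim, no loss.** C is uniform on 0 to 32.5 months, so solve 2^(−t/m) × (1 − t/32.5) = 0.5. The share still on treatment is [m/(32.5 ln 2)] × [1 − 2^(−32.5/m)].

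| True median (months) | Still on treatment | Plain median (months) | Error in median |
|---|---|---|---|
| 2 | 8.9% | 1.83 | −8% |
| 3 | 13.3% | 2.63 | −12% |
| 4 | 17.7% | 3.37 | −16% |

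**Closure 12 months after last enrolment, no loss.** C is uniform on 12 to 44.5 months. For t below 12, P(C > t) = 1, so the plain median equals m and is unbiased. The share still on treatment, and so the fall in the mean, is [m/(32.5 ln 2)] × [2^(−12/m) − 2^(−44.5/m)] = 0.1%, 0.8% and 2.2%.

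**Closure, with the 20% loss acting at a constant rate during treatment.** The loss rate is −ln(0.8)/12 = 0.0186 per month. The plain median is ln 2/(ln 2/m + 0.0186) = 1.90, 2.78 and 3.61 months, which is −5%, −7% and −10%. The mean falls by 5%, 8% and 11%.

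**Shorter follow-up.** The milestones in section 6 put last patient last visit in Q1 2017, 5 to 8 months after last enrolment. The median results above do not change, since all medians considered lie below 5 months. At 5 months and no loss the mean would be 1.6%, 4.2% and 7.4% low.

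**Who is affected at the interim.** Among patients still on treatment, the share enrolled in the previous 6 months is [1 − 2^(−6/m)]/[1 − 2^(−32.5/m)] = 87.5%, 75% and 65%. They are mostly recent entrants.

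**The case against.** The strongest objection is that section 9.7.1 leaves derived variables and missing data to the SAP, and that last dose minus first dose + 1 is a legitimate descriptive measure of exposure. This stands in part: observed exposure is worth reporting, and a SAP could add a censoring rule. But the protocol itself chooses both the formula and the summary method, and reserves Kaplan-Meier for the other intervals. A SAP that follows it inherits the mismatch with the definition in 9.1.2.

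The 20% in section 9.5 is also not loss on treatment. Survival follow-up continues after therapy ends, and loss at that stage does not affect duration. This stands: the 5 to 10% is conditional on an assumption that the protocol does not make. Section 9.7.1 does not say, either, that duration will be reported in July 2016, and a final analysis would supersede any interim figure.

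A reader might infer three stronger things, which the documents do not support:

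- **That unfinished patients are dropped.** In the same model without loss, a summary of completed patients only would put the median 9 to 19% low at the interim and 0 to 3% low at closure. But section 9.7.1 includes every treated patient and Table 2 records a last dose date at end of observation, so truncation is the likelier handling.
- **That the longest-treated patients are the ones affected.** At the interim they are mainly recent entrants.
- **That Kaplan-Meier has no drawback.** It assumes that loss on treatment is non-informative. If patients are lost because they deteriorated or stopped, it may overestimate duration.

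**Conclusion.** The point holds, and it is minor. The protocol defines duration to permanent discontinuation but fixes a summary that counts unfinished treatment as complete; the error is downward or nil. It matters mainly if duration is reported at the July 2016 interim. At closure with full follow-up and no loss on treatment it is negligible for the median and slight for the mean; any larger error at closure depends on how much loss occurs on treatment, which the protocol does not state. All sizes rest on assumed exponential durations, the 2 to 4 month range for the true median, uniform accrual and truncation as the handling.

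**What to change.** In sections 9.1.2, 9.7.3 and 9.7.5, add a Kaplan-Meier estimate of time to permanent discontinuation for any reason, including death, with median, quartiles and 95% confidence intervals. Censor patients who are ongoing or lost on treatment at their last known dosing date. Report how many patients are ongoing and how many are lost on treatment at each analysis that shows duration. Keep the plain summary of last minus first dosing date + 1, labelled as observed exposure.

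The cost is a few sentences and one extra analysis with methods already planned for OS, PFS and TTP; no new data are needed. State the non-informative censoring assumption beside the result; the count lost on treatment lets a reader judge how much rests on it.
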